Annex 1- COMORBIDITIES' LIST

(SELF-REPPORTED BY THE PARTICIPANTS AND REVEALED BY THEIR MEDICATION LIST)

COMORBIDITIES	Check if the condition is present	Check if you think that the condition affects significantly the person's functional status
ARTERIAL HYPERTENSION		
DYSLIPIDEMIA		
DIABETES MELLITUS		
ISCHEMIC HEART DISEASE		
CHRONIC ATRIAL FIBRILLATION/PAROXYSMAL AF OR OTHER ARRYTHMIA		
HEART INSUFFICIENCY		
STROKE OR TIA		
CHRONIC RENAL DISEASE		
RESPIRATORY DISEASE		
CANCER		
IMPAIRED COGNITIVE FUNCTION		
PARKINSON'S DISEASE		
EPILEPSY		
DEPRESSIVE EMOTION		
ANXIETY AND/OR SLEEP PROBLEM		
URINARY INCONTINENCE		
PROSTATE PATHOLOGY		
ANEMIA		
ARTHRALGIES- MUSCULOSCELETAL COMPLAINTS/DISEASES		

Annex 2: List of lead co-morbidities with special interest for the study:

CONDITION	Check if the condition is present (check all that apply)	Checkthesinglecondition with the mostimportantimportantimpactonthisindividual'sfunction(according toclinical evaluation)
Prior stroke		
MCI		
Osteoporosis if woman		
Osteoarthritis of man		
None of the above		

Annex 3- List of medication

ACTIVE SUBSTANCE	Number of administrations per day
(or commercial drug name)	(In case of missing information ="I don't know", enter the value 999.
	In case of use as needed (for example when in pain, insomnia etc), enter the value 888
	In case of administration frequency regular but lower than once daily, enter the value 777

1 UNIT	1.5 UNITS	2 UNITS	3 UNITS	9 UNITS	30 UNITS
Normal beer half pint (284ml) 4%	Small glass of wine (125ml) 12.5%	Strong beer half pint (284ml) 6.5%	Strong beer Large bottle/can (440ml) 6.5%	Bottle of wine (750ml) 12.5%	Bottle of spirits (750ml) 40%
Single spirit shot (25ml) 40%	Alcopops bottle (275ml) 5.5%	Normal beer Large bottle/can (440ml) 4.5%	Large glass of wine (250ml) 12.5%	consumptio	dvises alcohol n should not v exceed: Women 2-3 units daily
Source: ONS, NHS		Medium glass of wine (175ml) 12.5%			

Annex 4- alcohol units' equivalences

Annex 5- Mini Nutritional Assessment

Mini Nutritional Assessment **MNA**[®]

Last name:	e: First name:			
Sex	Age:	Weight, kg:	Height, cm:	Date:
	by filling in the boxes with the a ne screen. If score is 11 or less		sessment to gain a Malnutrition Indicate	or Score.
creening			J How many full meals does the 0 = 1 meal	e patient eat daily?
	declined over the past 3 mo stive problems, chewing or s		1 = 2 meals 2 = 3 meals	
0 = severe decre	ase in food intake crease in food intake in food intake		 K Selected consumption market At least one serving of dairy pr (milk, cheese, yoghurt) per day Two or more servings of legum 	oducts y yes no [
0 = weight loss gr 1 = does not know	etween 1 and 3kg (2.2 and 6.6	bs)	or eggs per week • Meat, fish or poultry every day 0.0 = if 0 or 1 yes 0.5 = if 2 yes 1.0 = if 3 yes	yes 🗌 no [
Mobility 0 = bed or chair b 1 = able to get ou 2 = goes out	ound t of bed / chair but does not go	out	L Consumes two or more servi per day? 0 = no 1 = yes M How much fluid (water, juice,	
past 3 months?	ychological stress or acute d 2 = no	isease in the	consumed per day? 0.0 = less than 3 cups 0.5 = 3 to 5 cups 1.0 = more than 5 cups	□.
Neuropsycholog 0 = severe dementia 1 = mild dementia 2 = no psycholog	ntia or depression		N Mode of feeding 0 = unable to eat without assist 1 = self-fed with some difficulty 2 = self-fed without any probler	
Body Mass Index 0 = BMI less than 1 = BMI 19 to less 2 = BMI 21 to less 3 = BMI 23 or gre	s than 21 s than 23	it in m) ²	O Self view of nutritional status 0 = views self as being malnou 1 = is uncertain of nutritional st 2 = views self as having no nut	rished ate ritional problem
2-14 points: -11 points:	ubtotal max. 14 points) Normal nutritional status At risk of malnutrition Malnourished		P In comparison with other per the patient consider his / her 0.0 = not as good 0.5 = does not know 1.0 = as good 2.0 = better	
or a more in-depth	assessment, continue with que	stions G-R	Q Mid-arm circumference (MAC) in cm

Assessment

G Lives inde	pendently (not in nur	sing home or hospit	al)
1 = yes	0 = no		
H Takes mor	e than 3 prescription	drugs per day	
0 = yes	1 = no		

н	H Takes more than 3 prescription drugs per day		
	0 = yes	1 = no	
	-		

IPressure sores or skin ulcers0 = yes1 = no

- References 1. Vetas B, Villars H, Abetlan G, et al. Overview of the MNA® Its History and Challenges. J Nutr Health Aging. 2006; 10:456-465. 2. Rubenstein LZ, Harter JO, Salva A, Guigoz Y, Vetlas B, Screening for Undernutrition in Genätz Forsciec: Developing the Short-Form Mini Nutritional Assessment (MNA-SF). J. Geront. 2001; 96 4: M366-377. 3. Guigoz Y. The Mini-Nutritional Assessment (MNA[®], Review of the Literature What does it tell us? J Nutr Health Aging. 2006; 10:466-487. © Société des Podulás Nestle, S.A., Vevey, Swatzeland, Trademark Owners © Nestlé, 1994, Revision 2009. N67200 12/99 10M For more information: www.mna-eliderly.com

 or eggs per week Meat, fish or poultry ex 		yes no
	verv dav	ves 🗌 no 🗌
0.0 = if 0 or 1 yes	, , ,	,
0.5 = if 2 yes		
1.0 = if 3 yes		
L Consumes two or mo per day?	ere servings of frui	it or vegetables
0 = no 1 = ye	es	
M How much fluid (wate consumed per day?	er, juice, coffee, te	a, milk) is
0.0 = less than 3 cups		
0.5 = 3 to 5 cups 1.0 = more than 5 cups	_	
1.0 = more than 5 cups	5	L.L
N Mode of feeding		
0 = unable to eat witho		
1 = self-fed with some 2 = self-fed without any		
O Self view of nutritiona		
0 = views self as being		
1 = is uncertain of nutron 2 = views self as having 1 = views sel		
2 = views self as navin	g no nutnitonal pro	biem
P In comparison with o the patient consider I		
0.0 = not as good		
0.5 = does not know		
1.0 = as good		
1.0 = as good 2.0 = better		□.□
1.0 = as good 2.0 = better Q Mid-arm circumferen		0.0
1.0 = as good 2.0 = better Q Mid-arm circumferen 0.0 = MAC less than 2		
1.0 = as good 2.0 = better Q Mid-arm circumference 0.0 = MAC less than 2 0.5 = MAC 21 to 22	1	
1.0 = as good 2.0 = better Q Mid-arm circumferen 0.0 = MAC less than 2 0.5 = MAC 21 to 22 1.0 = MAC greater that	1 n 22	.
1.0 = as good 2.0 = better Q Mid-arm circumferen 0.0 = MAC less than 2 0.5 = MAC 21 to 22 1.0 = MAC greater that R Calf circumference (C	1 n 22	
1.0 = as good 2.0 = better Q Mid-arm circumferent 0.0 = MAC less than 2 0.5 = MAC 21 to 22 1.0 = MAC greater that R Calf circumference (0 0 = CC less than 31	1 n 22	
1.0 = as good 2.0 = better Q Mid-arm circumferen 0.0 = MAC less than 2 0.5 = MAC 21 to 22 1.0 = MAC greater that R Calf circumference (C	1 n 22	
1.0 = as good 2.0 = better Q Mid-arm circumferent 0.0 = MAC less than 2 0.5 = MAC 21 to 22 1.0 = MAC greater that R Calf circumference (0 0 = CC less than 31	1 n 22 CC) in cm	
1.0 = as good 2.0 = better Q Mid-arm circumferen 0.0 = MAC less than 2 0.5 = MAC 21 to 22 1.0 = MAC greater that R Caff circumference (C 0 = CC less than 31 1 = CC 31 or greater Assessment (max. 16 pc	1 n 22 CC) in cm	
1.0 = as good 2.0 = better Q Mid-arm circumforem 0.0 = MAC less than 2 0.5 = MAC 21 to 22 1.0 = MAC greater that R Caff circumforence (C 0 = CC less than 31 = CC 31 or greater Assessment (max. 16 pc Screening score	1 n 22 CC) in cm Dints)	
1.0 = as good 2.0 = better Q Mid-arm circumferen 0.0 = MAC less than 2 0.5 = MAC 21 to 22 1.0 = MAC greater than Q = CA less than 31 1 = CC 31 or greater Assessment (max. 16 pc	1 n 22 CC) in cm Dints)	
1.0 = as good 2.0 = better Q Mid-arm circumferen 0.0 = MAC less than 2 0.5 = MAC 21 to 22 1.0 = MAC greater than 0 = CC less than 31 1 = CC 31 or greater Assessment (max. 16 pc Screening score Total Assessment (max.	1 n 22 CC) in cm Dints) . 30 points)	
1.0 = as good 2.0 = better Q Mid-arm circumferent 0.0 = MAC less than 2 0.5 = MAC 21 to 22 1.0 = MAC greater that R Calf circumference (for a constraint) 0 = CC less than 31 2 CC start and the constraint of the co	1 n 22 CC) in cm D ints) . 30 points)	
1.0 = as good 2.0 = better Q Mid-arm circumferen 0.0 = MAC less than 2 0.5 = MAC 21 to 22 1.0 = MAC greater than R Calf circumference (C 0 = C less than 31 1 = CC 31 or greater Assessment (max. 16 pc Screening score Total Assessment (max. Mainutrition Indicator Sc 24 to 30 points	1 1 22 CC) in cm Dints) . 30 points) core	
1.0 = as good 2.0 = better Q Mid-arm circumferen 0.0 = MAC less than 2 0.5 = MAC 21 to 22 1.0 = MAC greater that R Calf circumference (Compared to the strans 1) 0.0 = CC 31 or greater Assessment (max. 16 pc Screening score	1	

Index of In	Index of Independence in Activities of Daily Living (Katz Index of ADL)	y Living
Patient's Name:		Date:
Instructions: For each area of functioning listed below, cl Data recorded on the evaluation form is converted into an	Instructions: For each area of functioning listed below, check the description that applies. (The word "assistance" means supervision, direction, or personal assistance.) Data recorded on the evaluation form is converted into an overall ADL grade with the aid of definitions in the table on the following page.	ns supervision, direction, or personal assistance.) e following page.
BATHING – either sponge bath, tub bath, or shower		
□ Receives no assistance (gets in and out of tub by self if tub is usual means of bathing)	□ Receives assistance in bathing only one part of the body (such as back or a leg)	Receives assistance in bathing more than one part of the body (or not bathed)
DRESSING - gets clothes from closets and drawers - inclu	DRESSING – gets clothes from closets and drawers – including underclothes, outer garments, and using fasteners (including braces, if worn)	uding braces, if worn)
Gets clothes and gets completely dressed without assistance	Gets clothes and gets dressed without assistance except for assistance in tying shoes	Receives assistance in getting clothes or in getting dressed, or stays partly or completely undressed
TOILETING – going to the "toilet room" for bowel and urine	TOILETING – going to the "toilet room" for bowel and urine elimination, cleaning self after elimination, and arranging clothes	thes
Goes to "toilet room," cleans self, and arranges clothres without assistance (may use object for support such as cane, walker, or wheelchair and may manage night bedpan or commode, emptying same in morning)	Receives assistance in going to "toilet room" or in cleaning self or in arranging clothes after elimination or in use of night bedpan or commode	Doesn't go to room termed "toilet" for the elimination process
TRANSFER	I	I
Moves in and out of bed as well as in and out of chair without assistance (may be using object for support such as cane or walker)	Moves in and out of bed or chair with assistance	Doesn't get out of bed
CONTINENCE	C	C
Controls urination and bowel movement completely by self	Has occasional "accidents"	Supervision helps keep urine or bowel control, catheter is used, or is incontinent
FEEDING	I	ſ
Feeds self without assistance	☐ Feeds self except for getting assistance in cutting meat or buttering bread	Receives assistance in feeding or is fed partly or completely by using tubes or intravenous fluids
(Kalz et al., 1963)		_

Annex 6- Activities of Daily Living

Annex 7- Instrumental Activities of Daily Living

Instrumental Activities of Daily Living	For each item check the one that applies	Grading
Ability to Use Telephone		
Operates telephone on own initiative; looks up and dials numbers.		1
Dials a few well-known numbers.		1
Answers telephone, but does not dial		1
Does not use telephone at all		0
I do not know		
Shopping		
Takes care of all shopping needs independently		1
Shops independently for small purchases		0
Needs to be accompanied on any shopping trip		0
Completely unable to shop		0
I do not know		
Food Preparation		
Plans, prepares, and serves adequate meals independently		1
Prepares adequate meals if supplied with ingredients		0
Heats and serves prepared meals or prepares meals but does not maintain adequate diet		0
Needs to have meals prepared and served		0
Non applicable-never used to do this		
I do not know		
Housekeeping		
Maintains house alone with occasion assistance (heavy work)		1
Performs light daily tasks such as dishwashing, bed making		1
Performs light daily tasks, but cannot maintain acceptable level of cleanliness		1

1
0
•
1
1
0
1
1
1
0
0
1
0
0
1

track of income	
Manages day-to-day purchases, but needs help with banking, major purchases, etc .	1
Incapable of handling money	0
Non applicable-never used to do this	
I do not know	

[figure not shown]
Annex 8a- The Mini Mental State Examination Scale

. ORIENTATION (Ask the	Record Each Answer:	(Maximum Score = 10)
following questions; correct = \square) What is today's date?	Date (eg, May 21)	1 🗆
What is today's gate?	Year	1 🗆
What is the month?	Month	1 🗆
What day is today?	Day (eg, Monday)	1 🗆
Can you also tell me what season it s?	Season	1 🗆
Can you also tell me the name of this hospital/clinic?	Hospital/Clinic	1 🗆
What floor are we on?	Floor	1 🗆
What city are we in?	City	1 🗆
What county are we in?	County	1 🗆
What state are we in?	State	1 🗆
II. IMMEDIATE RECALL	(correct = ☑)	(Maximum Score = 3)
Ask the subject if you may test	Ball	1 🗆
his/her memory. Say "ball, "flag," "tree" clearly and slowly, about on	Flag	1 🗆
second for each. Then ask the subject to repeat them. Check the box at right for each correct response. The first repetition determines the score. If he/she does not repeat all three correctly, keep saying them up to six tries until he/she can repeat them	Tree	I D
III. ATTENTION AND CALCULATION		
A. Counting Backwards Test	(Record each response, correct = ☑)	(Maximum Score = 5)
Ask the subject to begin with 100	93	1 🗆
and count backwards by 7. Record each response. Check one box at	86	1 🗆
right for each correct response. Any	79	1 🗆
response 7 or less than the previous response is a correct response. The score is the number of correct subtractions. For example, 93, 86,	72	
80, 72, 65 is a score of 4; 93, 86, 78 70, 62, is 2; 92, 87, 78, 70, 65 is 0.	65	1 🗆
V. RECALL	(correct = ☑)	(Maximum Score = 3)
Ask the subject to recall the three	Ball	1 🗆
words you previously asked him/her to remember. Check the Box at right	Flag	1 🗆
or each correct response.	Tree	1 🗆
V. Language	$(correct = \square)$	(Maximum Score = 9)
Naming	Watch	1. 🗆
Show the subject a wrist watch and ask him/her what it is. Repeat for a pencil.	Pencil	1 🗆
Repetition		
Ask the subject to repeat "No, ifs, ands, or buts."	Repetition	1 🗆
Three -Stage Command		
stablish the subject's dominant	Takes paper in hand	1 🗆
hand. Give the subject a sheet of blank paper and say, "Take the	Folds paper in half	1 🗆
paper in your right/left hand, fold it n half and put it on the floor."	Puts paper on floor	1 🗆
Reading		
Hold up the card that reads, "Close your eyes." So the subject can see it clearly. Ask him/her to read it and do what it says. Check the box at right only if he/she actually closes his/her eyes.	Closes eyes	
Writing		
Sive the subject a sheet of blank paper and ask him/her to write a sentence. It is to be written ponataneously. If the sentence contains a subject and a verb, and is ensible, check the box at right. Correct grammar and punctuation are not necessary.	Writes sentence	1 🗆
Copying		[
how the subject the drawing of the intersecting pentagons. Ask him/her o draw the pentagons (about one nch each side) on the paper rovided. If ten angles are present nd two intersect, check the box at ight. Ignore tremor and rotation.	Copies pentagons	
DER	IVING THE TOTAL SC	ORE
Add the number of cor		TOTAL SCORE

[figure not shown]
Annex 8b- MMSE item 28

CLOSE YOUR EYES

Annex 8c- MMSE item 30

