2.2 Participants' characteristics

The Clinical study will be performed in 3 Clinical Centers: University of Patras (UoP), Greece; INSERM-Nancy, France; and MATERIA- Nicosia, Cyprus. Each Center will recruit 170 individuals for the FrailSafe study. By this way a total of 510 community living subjects aged 70 years and older will be recruited. The inclusion and non-inclusion criteria are demonstrated in table 1.

Table 1. Inclusion and exclusion criteria

Inclusion criteria
Age ≥70 years
Informed consent provided
Exclusion criteria
Lack of wish to participate
Consent withheld
Inability to give consent because of incapacity
Inability to walk
Inability to speak Greek or French (see clinical centers)
Diagnosis of clinically significant cognitive impairment or score less than 24 on the Mini– Mental State Examination
Diagnosis of advanced malignancy, other terminal illness or an estimated life expectancy of less than 12 months
Active psychiatric disorder based on medical records or clinical opinion at the time of recruitment, current substance users, or excessive alcohol drinkers.

The numerical threshold for "older age" has always been controversial, though most widely accepted was the age of 65 years, corresponding in the usual age of retirement. Still, nowadays "young old" individuals maintain a good general health condition and with the exception of special cases, frailty is most likely to be encountered in older age ranges. In the FrailSafe study, since we need to include people in non-frail, pre-frail, as well as frail conditions, it was decided that the age threshold will be that of 70 years.

In order to be able to comply better with the requirements of the study (usage of technical material, cooperation for the testing of novel equipment, need for participant's feedback and relatively long follow up period), subjects with highly debilitating conditions, such as inability to walk, presence of clinically significant cognitive impairment, or active psychiatric

disorder will be excluded from the study. Similarly, subjects with serious medical conditions that convey a guarded prognosis (estimated life expectancy of less than 12 months) will be excluded as well.

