3.1.10 Assessment subset 10: Cognitive, mood and sleep evaluation

This session includes the following parts:

Global cognitive function evaluation. The Mini Mental State Examination (MMSE) test is employed (23), (annex 8), available in translated and validated versions in both French and Greek (24, 25). This scale is the most widely used instrument of global assessment of cognitive function both in clinical, epidemiological and research settings. It is useful as a screening tool in order to detect a cognitive dysfunction and to follow up its evolution, but it lacks specificity to distinguish between certain forms of dementia and sensitivity to discriminate a mild dysfunction in an early stage (26). Moreover it is highly influenced by the age and educational level (27, 28). A cut off score of below 24 during the first evaluation is used as an exclusion criterion for the present study, in order to avoid recruiting participants with important cognitive problems who are less likely to be able to use in an optimal way the FrailSafe system's devices and applications and to be apt for the follow up period.

To overcome the inherent inability of MMSE to detect more discreet cognitive dysfunctions and to augment the sensitivity of cognitive testing in highly educated older adults, the Montreal Cognitive Assessment (MoCA, annex 9) is also employed. The latter is a brief cognitive screening tool for the detection of MCI (29, 30, 31), available in multiple languages, among which the French and Greek. Since MCI is an important morbidity for our study, this scale will contribute to its detection.

- Memory complaint's detection. The expression of a memory complain from an older subject could be an indication of early sings of cognitive dysfunction (32), although there is not global consistency in this finding in the literature (33). Still, the general tendency is that subjective memory complains merit further evaluation (34, 35).
- Depression screening. The 15-items' Geriatric Depression Scale (GDS) (36) (annex10) is used in order to detect subjects with possible depression. This scale cannot pose the definitive diagnosis of depression, even though there is some evidence that it can detect a major depressive episode (37). Still it can be used to screen for depressive symptoms (38). It is available in both Greek in a validated version (39) and in French (40).

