5.2.2 Proxy outcomes

Due to the limited number of participants, the tight timeframe of the project and the frequency of occurrence of Hard Outcomes, we propose the use of proxy outcomes that we are confident that we will be able to measure and to use in the data analysis part of the project to draw some solid conclusions. The proxy outcomes could also be considered as a diagnostic, early detection tool of a declining condition that may lead to a hard outcome. By keeping a concise, short, practical yet informative track of the change in proxy outcomes we will be able via coaching and interventions to postpone the inevitable occurrence of a Hard outcome, thus improving prognosis and quality of life.

Repeated clinical evaluations are carried out in the following domains: physical, cognitive, psychological, nutritional, and wellness. Loss of function in each domain can indirectly describe loss of physiological reserve, which underscores frailty, and consequently the adverse events of frailty (described above in 5.2.1). The clinical experts of this consortium in a consensus meeting have agreed on a key clinical assessment of each domain, which best describes loss of reserve and is believed to predict adverse outcome.

Therefore, as proxy outcomes have been selected the following:

- Gait speed (Physical Domain)
- MoCA and/or MMSE (Cognitive Domain)
- GDS (Psychological Domain)
- Weight loss (Nutritional Domain)
- Health status self-assessment (General health/Wellness Domain)

The clinicians in the process of selecting a proxy outcome in each domain made use of the bibliography and their expert opinion. At the end of the clinical studies, analysis will be carried out correlating these proxy outcomes to the hard outcomes observed in participants and, if possible, explore validity and reliability.

Review of the bibliography showed that gait speed test has been established as the test with the strongest correlation to frailty (72), and has been linked with the hard outcomes, such as falls and mortality (73,74). Reduced MoCA and MMSE scores, though the later to a lesser extent as less sensitive to the detection of mild cognitive decline, have been linked both with

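### Annex 8a: the MMSE serial-sevens rule, the printed series and the three worked scores cannot all hold under any plain reading

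*Protocol*

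**What the plan says.** Annex 8a prints the MMSE form. In the attention and calculation item the subject counts down from 100 in sevens, for 0 to 5 points ("Maximum Score = 5"). The rater is given three cues:

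- **A rule.** Any "response 7 or less than the previous response is a correct response", and "The score is the number of correct subtractions".
- **A printed series.** The values 93, 86, 79, 72, 65 stand one beside each tick box.
- **Three worked scores.** "80, 72, 65 is a score of 4; 93, 86, 78 70, 62, is 2; 92, 87, 78, 70, 65 is 0". The first string begins with 93 and 86 on the preceding line, so it reads 93, 86, 80, 72, 65.

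The total is used in three places. Table 1 in section 2.2 lists as an exclusion "Diagnosis of clinically significant cognitive impairment or score less than 24 on the Mini– Mental State Examination", and section 3.1.10 repeats it: "A cut off score of below 24 during the first evaluation is used as an exclusion criterion for the present study". Section 5.2.2 lists "MoCA and/or MMSE (Cognitive Domain") among the proxy outcomes. Table 22 in Appendix I makes the MMSE score a component of the Clinical Frailty Index. The executive summary presents the annexes as the questionnaires that will actually be administered. Section 3.1.10 adds that validated French and Greek versions of the MMSE exist; they are not reproduced.

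**The concern.** The study runs in three centres and repeats the clinical evaluation over time. If the form's rule, tick boxes and examples point to different scores, two raters can score the same answers differently, and so can one rater at two visits.

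Two things are at stake. At entry, one point decides between 23 and 24, and section 3.1 has a subject below 24 leave the study and be replaced. In follow-up, a change of scoring habit between visits would enter the data as a change in cognition. Section 5.2.2 fits a time curve to each proxy variable and sets the quadratic term to zero when fewer than three time points exist. Groups C and D have only two clinical evaluations (M31 and M36), so any scoring difference between those visits would go entirely into the fitted slope.

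**Working it through.** **Inputs.** All come from Annex 8a: the rule, the series 93, 86, 79, 72, 65, and the three strings with their stated scores 4, 2, 0.

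**Step 1: successive differences, starting from 100.**

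- Example 1 (93, 86, 80, 72, 65): 7, 7, 6, 8, 7
- Example 2 (93, 86, 78, 70, 62): 7, 7, 8, 8, 8
- Example 3 (92, 87, 78, 70, 65): 8, 5, 9, 8, 5

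**Step 2: score each string under each reading.**

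| Reading | Ex. 1 | Ex. 2 | Ex. 3 |
|---|---|---|---|
| Stated on the form | 4 | 2 | 0 |
| A: exactly 7 below the previous answer | 3 | 2 | 0 |
| B: matches the printed series | 4 | 2 | 1 |
| C: step of 7 or less (literal wording) | 4 | 2 | 2 |

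A fails only example 1, by 1 point. B fails only example 3, by 1 point. C fails only example 3, by 2 points. Example 2 agrees under all three.

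**Step 3: other readings.** None of these returns 4, 2, 0 either:

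- step of 7 or more: 4, 5, 3
- any lower number: 5, 5, 5
- A or B: 4, 2, 1
- A and B together: 3, 2, 0
- printed series until the first error: 2, 2, 0
- a printed value in any position: 4, 2, 1

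**Step 4: size.** Across A, B and C the same answers score 3 or 4 in example 1, and 0, 1 or 2 in example 3. Neither figure is a ceiling. The string 92, 85, 78, 71, 64 has steps 8, 7, 7, 7, 7, so it scores 4 under A and C but 0 under B. The string 93, 86, 79, 72, 65 scores 5 under all three.

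**Step 5: the cut-off, for illustration.** The form's parts sum to 10 + 3 + 5 + 3 + 9 = 30, so the other items contribute up to 25. Assume a person scores 20 on them and gives the answers of example 1. The total is 20 + 3 = 23 under A (excluded) and 20 + 4 = 24 under B or C (eligible). Assume instead 23 on the other items and the answers of example 3. The total is 23 under A, 24 under B and 25 under C.

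**Step 6: a two-visit slope, for illustration.** From M31 to M36 is 5 months. If the two visits were scored under different readings, a 1-point gap would add 1/5 = 0.2 points per month to a person's fitted slope, and a 2-point gap 2/5 = 0.4.

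**The case against.** The strongest objection concerns reach. Annex 8a is an English form that asks for the county and the state, while Table 1 requires participants to speak Greek or French. If the centres used the validated translations with a clear rule of their own, field scores may be unaffected. This stands as a limit on the consequence, because those forms are not shown. It does not remove the error, since the protocol presents its annexes as the instruments in use and no other section gives a rule that settles the conflict.

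Four further inferences are tempting and not supported:

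- **That no rule whatever fits.** Unstated rules can be built to fit; counting steps of 6 or 7 gives 4, 2, 0. The form states no such rule, so the claim is limited to plain readings. Reading B is also only implied: the text defines correctness by the previous answer, and the boxes merely suggest a match to the series.
- **That 1 to 2 points is a bound or an expected effect.** It describes the form's own examples only.
- **That the artefact is as large as a true cognitive change.** The protocol gives no MMSE standard deviation, expected decline or minimal important change to compare it with.
- **That the cognitive proxy outcome as a whole is compromised.** It may be MoCA, MMSE or both, and MoCA is untouched. Section 5.2.2 itself calls MMSE the less sensitive of the two to mild decline.

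**Conclusion.** Wrong as written. The rule, the printed series and the worked scores in Annex 8a are mutually inconsistent under every plain reading, and the arithmetic can be checked by hand. On the form's own first and third examples the discrepancy is 1 to 2 points of 5.

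The consequence is conditional. Eligibility is affected only for people near 24 whose serial-sevens errors score differently between readings. The Clinical Frailty Index is affected through its MMSE item, and the proxy outcome only where MMSE is used. All of this assumes that the forms in use carry the same fault or that raters relied on Annex 8a, which the document does not show. Nor does it show which of the three cues is the mistaken one. It merits correction because the total feeds an exclusion and longitudinal measures, but there is no evidence here that recorded scores are wrong.

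**What to change.** 1. Reconcile the rule, the printed values and the examples in Annex 8a so that one rule reproduces all three scores. The smallest repair consistent with "The score is the number of correct subtractions" is exactly 7 less than the previous answer: delete the word *or* from the rule and change the first example from 4 to 3. Another rule is acceptable if all three cues then agree.
2. Check which rule the French and Greek versions actually administered carry, and apply one rule at all centres and visits. Annex 8a alone is no ground for rewriting a validated translation.
3. The form asks the rater to record each answer. Where those answers were kept, rescore serial sevens for the longitudinal analyses.
4. Report, as a sensitivity matter, any enrolled participant whose entry total would cross 24 on rescoring.

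The cost is a short correction to the form and a simple rescoring routine. Some early MMSE totals may shift. Going from reading C to A can only lower or keep a score, because every step of exactly 7 is also a step of 7 or less; going from B to A can move it either way. The extent of any carry-over to the translated forms stays unknown until they are checked.
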